4.1 Study Overview

Phase I Clinical Trial, Controlled, Non-Comparative, Open-label, Single-Center

4.2 Rationale for the study design

The design of the study (clinical trial) is considered the highest standard of data quality when seeking to explore the effect of an intervention. The drug development phase (phase I) corresponds to the objective of the study, which is to evaluate safety and tolerability, so the intervention time is short and the sample size required is smaller than that of an efficacy clinical trial. Blinding in the study was not considered because there will be only one treatment group.

4.3 Expected duration

The total duration of the study, from the first visit of the first patient to the preparation of the final report, is estimated to be 6 months.

The planned recruitment period is 4 months. Considering that the proposed sample is 29 subjects, the total average recruitment rate during the study should be no less than 2 subjects included each week.

The approximate duration of each subject in the study is up to 22 days.

5. Study population

5.1 Eligibility Criteria

5.1.1 Inclusion criteria

- Be clinically healthy
- Can voluntarily give their signed informed consent (CRF)
- Be able and willing to comply with scheduled visits, treatment plan, and other study procedures
- Be between 18 and 35 years old.
- No history of contact lens use
- Women of childbearing potential must ensure continued use (initiated \geq 30 days prior to signing the CRF) of hormonal contraceptive or intrauterine device (IUD) use during the study period
- Have a better far-corrected visual acuity of 20/30 (logMAR 0.2) or better in both eyes.
- Have a better corrected visual acuity close to 20/25 (logMAR 0.1) or better in both eyes.
- Have vital signs within normal parameters.
- Have an IOP \geq 10 and \leq 21 mmHg.

5.1.2 Exclusion criteria:

- Be a user of topical ophthalmic products of any kind.
- Allergy or known intolerance to ingredients in atropine eye drops and other derivatives of muscarinic antireceptor agents.
- Being a user of medicines, or herbal products (plant extracts, infusions, naturopathic preparations, homeopathics, etc.), by any other means of administration.
- For women: being pregnant, breastfeeding, or planning to become pregnant within the study period.
- Have participated in any investigational clinical study 90 days prior to inclusion in the present study.
- Have previously participated in this same study.
- Who are unable to follow the lifestyle considerations described in Annex 1.
- Have a history of any chronic-degenerative disease, including diabetes and high blood pressure.
- Have an active inflammatory or infectious disease at the time of study entry.
- Have unresolved injuries or trauma at the time of study entry.
- Have a history of any type of eye surgery.
- Having undergone surgical, non-ophthalmologic procedures within the past 3 months.
- Be or have an immediate family member (e.g., spouse, parent/legal guardian, sibling, or child) who is employed by the research site or sponsor, and who is directly involved in this study.
-

5.2 Criteria for elimination and/or substitution of subjects

5.2.1 Elimination Criteria

- Withdrawal of the letter from the FCI.
- Presentation of a serious adverse event related or not to the investigational product, which at the discretion of the PI and/or sponsor could affect the patient's ability to continue with the study procedures safely.
- No tolerability or hypersensitivity to any of the compounds used during the tests (fluorescein, lysmine green or tetracaine).
- No tolerability or hypersensitivity to any of the investigational drugs.
- Adherence < 90% determined by the subject's diary

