6.1.3 Treatment with the investigational product

The investigational product will be delivered at the conclusion of the baseline visit, and the investigational subject will administer the drops at night, applying a total of one drop at night to each eye during the 14 days of application.

The baseline visits and visit 1 should be done in the morning shift, before 4:00 p.m., so that the patient can have enough time to apply PRO-201 at the indicated time.

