6.4 Procedure for monitoring and measuring adherence

For more than four decades, there has been a lot of research on the appropriate way to measure and quantify medication adherence, but none has reached a consensus to stand as the gold standard, both in cross-sectional and longitudinal studies. [27, 28, 29, 30, 31, 32, 33, 34]

There are different procedures to measure adherence to pharmacological interventions. The most common procedure includes self-reports, which include patient interviews, questionnaires and self-monitoring diaries. Its strengths are speed, flexibility, low cost and ease of implementation; They have a high degree of specificity for non-adherence, however, the sensitivity and reliability for adherence is low. [34, 35]

The biochemical measurement of the drug, or its metabolite, is one of the methods that best confirms the use of the drug. However, in addition to raising costs and being impractical, it is of little use in the context of ophthalmic applications, since concentrations at the peripheral level could be undetectable; and samples of other tissues involve more invasive methods that would not be advisable. [34]

There is no standardized parameter to define adequate adherence, it must be defined and delineated by the objectives of the research. [34]

For this study, a minimum adherence of 90% (per subject's diary) will be necessary to meet the objectives of the research. Therefore, subjects with adherence of less than 90% will not be considered for the evaluation of exploratory variables but will be considered for the safety and tolerability variables in the intention-to-treat population group.

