10.3.2 Safety and tolerability analysis

10.3.2.1 Analysis for Primary Variables

An analysis of safety and tolerability outcomes will be carried out in the safety population, defined as any subject who has received at least one dose of the investigational product (PRO-201) regardless of adherence to it or adherence to the protocol (intention-to-treat population, ITT).

The statistical analysis for the primary variables of a quantitative type will be estimated by means of the Kolmogorov-Smirnov statistic for the difference in measurements, once the values have been adjusted with respect to their baseline within everyone. In cases where applicable, the nonparametric Mann-Whitney U test will be used.

For conjunctival hyperemia, Pearson's X² or Fisher's exact test will be used at expected values less than 5.

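### Diary adherence below 90% is an elimination criterion in 5.2.1 but only an exploratory-analysis exclusion in 6.4; its period and unit are not stated, and Day 16/21 safety assessment of an eliminated subject is not guaranteed

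*Combined protocol and SAP*

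**What the plan says.** Section 5.2.1, repeated in the synopsis (1.1), includes among the elimination criteria: "Adherence < 90% determined by the subject's diary". It stands in the same list as withdrawal of consent, serious adverse events and intolerance to the product.

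Section 6.4 gives the same threshold a narrower effect: "subjects with adherence of less than 90% will not be considered for the evaluation of exploratory variables". It adds that they "will be considered for the safety and tolerability variables in the intention-to-treat population group". Section 10.3.2.1 agrees with 6.4. The primary population is every subject with at least one dose, "regardless of adherence to it or adherence to the protocol". Section 10.3.3 analyses the exploratory variables in a per-protocol set.

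On timing, the schedules in 1.3 and 7.6.2 mark an adherence assessment at visit 1 and at the final visit, but return and evaluation of the diary at the final visit only. Section 7.5.13 describes adherence as the applications made in the interval between visits.

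On follow-up, 5.5 treats the visit at which withdrawal is determined as the final visit (the wording is unclear in translation). It provides continued follow-up, until the event closes, for subjects removed because of adverse events. The synopsis sets both primary assessments at Days 7, 16 and 21. Section 10.4 states that missing data are not imputed.

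**The concern.** The same subject is to be eliminated under one section and kept for the primary analysis under two others. One can reconcile them by saying that elimination ends participation while the data stay in the analysis, but the documents do not say so, and that reading brings its own difficulty. A subject whose participation ends at visit 1 would remain in the denominator of both primary incidences without the two later scheduled assessments. With no imputation rule, an event that nobody asked about would in practice be counted as no event.

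Because period and unit are missing, two people applying the criterion in good faith could reach opposite decisions on identical diaries.

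The numbers are small enough for this to matter. The limits in 3.2 are 10% for unexpected related adverse events and 15% for photophobia. With 29 subjects, 2 events are 6.9% and 3 are 10.3%; 4 events are 13.8% and 5 are 17.2%. One unobserved event moves an incidence by 1/29 = 3.4 percentage points and can move it across its limit.

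**Working it through.** **The plan's own figure.** Section 10.1.2 raises 24 subjects by 20%: 24 × 1.20 = 28.8, rounded up to 29, an allowance of 5. The plan gives no count of missed applications corresponding to 90%, so that has to be derived.

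**Applications due.** From 6.1.3: "applying a total of one drop at night to each eye during the 14 days of application", so 14 nightly applications or 28 single drops. "The investigational product will be delivered at the conclusion of the baseline visit", so the first application falls on the night of Day 1. "The baseline visits and visit 1 should be done in the morning shift, before 4:00 p.m", so that day's application is still to come at visit 1. Visit 1 is Day 7 ± 1, so 6 − 1 = 5, 7 − 1 = 6 or 8 − 1 = 7 applications are due by then. The remaining 9, 8 or 7 fall between visit 1 and the final visit.

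**Adherence = (due − missed) / due.**

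| Period judged | One night missed (both eyes) | One drop missed (one eye) |
|---|---|---|
| To visit 1, Day 6 | 4/5 = 80.0% | 9/10 = 90.0% |
| To visit 1, Day 7 | 5/6 = 83.3% | 11/12 = 91.7% |
| To visit 1, Day 8 | 6/7 = 85.7% | 13/14 = 92.9% |
| Visit 1 to final visit (9, 8 or 7 due) | 88.9%, 87.5% or 85.7% | 94.4%, 93.8% or 92.9% |
| All 14 nights | 13/14 = 92.9% | 27/28 = 96.4% |

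On the between-visit period, one missed night always falls below 90% and one drop in one eye never does. On the full course, two missed nights are needed (12/14 = 85.7%), or three of 28 single drops (25/28 = 89.3%).

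**How many subjects.** The documents give no miss rate, so the rate q per night is an assumption, with misses taken as independent.

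- Judged at visit 1 on Day 7, P = 1 − (1 − q)^6. At q = 2%, 1 − 0.98^6 = 0.114, and 29 × 0.114 = 3.3 subjects. At q = 5%, 1 − 0.95^6 = 0.265, and 29 × 0.265 = 7.7.
- Judged on all 14 nights, P = 1 − (1 − q)^14 − 14q(1 − q)^13. At q = 2%, P = 0.031, or 0.9 subjects. At q = 5%, P = 0.153, or 4.4.
- Widening the assumption to 1% and 10% gives 1.7 and 13.6 at visit 1, against 0.2 and 12.0 over 14 nights.

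**What a subject eliminated at visit 1 would miss.** Of the three scheduled primary assessments, Day 7 has been made, while Days 16 and 21 are not guaranteed by 5.5, whose continued follow-up names only removals for adverse events. If the rule is applied at the final visit instead, the Day 16 assessment has been made and at most the Day 21 call is in question.

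**The case against.** The strongest reply is that the analysis is already protected: 6.4 and 10.3.2.1 keep every dosed subject in the primary analysis, and 10.3.3 already has a per-protocol set for the exploratory variables. That stands for membership of the analysis sets. It does not settle whether the later observations are collected.

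Three stronger conclusions are tempting, and the documents do not support them.

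- A reader might infer that a single missed drop at visit 1 eliminates a subject. No section says that elimination is decided at visit 1. The criterion rests on the diary, whose return and evaluation is scheduled only at the final visit, which points towards the full course. The visit 1 adherence assessment and 7.5.13 point the other way, so the timing is open. Nor does one drop missed in one eye breach the limit on any period.
- A reader might infer that elimination ends all adverse-event information. It does not. Adverse events are assessed at visit 1 itself, 8.5 requires identified events to be followed to their outcome, 7.7.5 allows unscheduled visits, and 5.5 has even subjects lost to follow-up asked about adverse events. What is unprotected is the scheduled detection of new events afterwards.
- A reader might infer that subjects who skip drops are the intolerant ones and are then counted as event-free. The documents draw no such link, and intolerance to the product is a separate elimination criterion. If a symptom led to missed applications before visit 1, it preceded the visit 1 questioning and can be recorded there. The qualification is that photophobia is elicited without directed questioning (7.4.5.4), so it may go unreported.

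**Conclusion.** The contradiction between 5.2.1 with the synopsis and 6.4 with 10.3.2.1 is in the text and must be reconciled. The missing period and unit are also established: one missed night is either a breach or not, depending on a choice the plan leaves open.

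The consequence for the primary endpoints is conditional. It requires that elimination for adherence takes place before the final visit and that 5.5 is then applied as written. In that case the subject is counted in both primary incidences on shortened observation, and the possible bias is downward. Its size cannot be given, because the documents contain neither a miss rate nor an event rate for the later period. The range of 3.3 to 7.7 of 29 against 0.9 to 4.4 counts subjects who would meet the criterion under an assumed 2% to 5% miss rate per night. It is not a forecast of eliminations or of lost events. At the upper end of that range the visit 1 reading would exceed the allowance of 5, and 5.2.2 does not list low adherence as a ground for replacement. That comparison matters only if such subjects are treated as losses, which 10.3.2.1 does not do.

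**What to change.** Reconcile 5.2.1 and the synopsis with 6.4 and 10.3.2.1 so that the 90% figure has one stated role. In the analysis that role is membership of the per-protocol set used for the exploratory variables. State the period over which it is calculated and whether the unit is a nightly application or a single drop.

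Add to 5.5 and 10.3.2.1 that adverse-event and photophobia data are collected through Day 21 on every dosed subject, whatever the adherence, unless consent is withdrawn. This concerns data collection and analysis sets only; whether a subject with low adherence goes on using the product is for the sponsor to settle when the sections are reconciled.

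The cost is wording and a few more follow-up contacts.

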5.2.2 Substitution of subjects

The sponsor, with the prior authorization of the research ethics committees, may decide to replace the subjects who withdraw their FCI or those who present loss of follow-up, until the necessary sample size is completed.

5.3 Counting failures

A screening failure is defined as those participants who agree to participate in the study, giving their consent, but who are not assigned to the treatment group, i.e., do not enter the study. It is necessary to report at least the following information on counting failures:

- Demographics.
- Details of the failure to count (specify whether it is due to eligibility criteria, which one, or some other reason for the failure).
- Presence of serious adverse events during the count.

This is necessary to comply with the CONSORT (*Consolidated Standards of Reporting Trials*) guidelines for the publication of results or to respond to possible questions from regulatory authorities.

5.4 Recruitment and retention strategies

The duration of the subject's participation in the study is approximately 21 days, during which time they must attend three visits in total and a safety call will be made, which corresponds to the baseline visits, visit 1, final visit and safety call. Strategies to improve subject retention include, but are not limited to:

- Clearly inform the objectives of the study.
- Make calls or send text messages to remind you of appointments or activities to do.
- Provide a printed calendar and an identification card to remember appointments and activities that will be carried out, in addition to the estimated time of their duration.

- Systematic organization of the study procedures, so that the subject does not last longer than necessary in his visit.
- Minimize subject wait times.

All materials to be delivered to the subject or recruitment strategies implemented by the center will be submitted for approval by the corresponding committees.

5.5 Procedure in case of early discontinuation

For this protocol, early discontinuation is defined as those subjects who were assigned to the PI, who at some points were active subjects of the study, but their final evaluation could not be completed.

If the subject does not terminate their participation due to withdrawal of consent or major deviation, the last visit, in which their withdrawal was determined, will be considered their final visit. Subjects who are removed due to the presence of AEs will continue with the follow-up that is defined until the closure of their AE.

In cases where the participating subject does not attend their appointment, the research center must make a call to find out the reason and will try to make a new appointment within the established window period or an unscheduled appointment. If it is not possible to make an appointment, the subject will be considered as loss of follow-up and will be asked about the presence of adverse events and the reason for leaving the study, as minimum data.

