
Elimination criteria:
 
 – Withdrawal of the letter from the FCI. – Presentation of a serious adverse event related or not to the investigational product, which at the discretion of the PI and/or sponsor could affect the patient's ability to continue with the study procedures safely. – Non-tolerability or hypersensitivity to any of the compounds used during the tests (fluorescein, lysmine green, tetracaine). – No tolerability or hypersensitivity to the investigational drug. – Adherence < 90% determined by the subject's diary 	

Research Product (PI):
 
 - PRO-201 . Atropine Sulfate 0.01%. Zapopan, Jalisco, Mexico. Ophthalmic solution Laboratorios Sophia, S.A. de C.V - Dosage: 1 drop once a day (QD) in the evening, in both eyes (AO). - Route of administration: Ophthalmic 	

Duration of treatment: 14 days
	
Duration of the subject in the study: 21 days

Evaluation criteria:
 
Primary outcome variables
 
 – Incidence of unexpected PI-related AEs (Time of Assessment [TE]: days 7, 16 and 21) – Incidence of IP-related photophobia. (TE: 7th, 16th and 21st) 
Secondary outcome variables:
 
 – Changes in pupillary diameter (ET: day 7 and 16). – Incidence of expected PI-related AEs (TE: days 7, 16, and 21). – Changes in visual acuity (TE: day 7 and 16). 
Exploratory variables:
 
 – Changes in the AVMC (TE: day 7 and 16). – Intraocular pressure (IOP) changes (ET: day 7 and 16). – Changes in corneal and conjunctival staining with fluorescein and lysmine green (ET: day 7 and 16). – Changes in vital signs (heart rate and blood pressure) (ET: day 7 and 16). – Changes in the OCI (TE: day 16). 	

Statistical methodology
 
The analysis of the data collected in the study will be carried out using the SPSS version 19.0 statistical package. For continuous and discrete quantitative variables, data will be expressed by
	

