7.7.4 Security Call

- Evaluation of adverse events

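### Section 5.5 classes a reachable subject as lost after one appointment that cannot be rebooked, and does not require the Day-16 and Day-21 adverse-event checks that both primary incidences rely on

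*Combined protocol and SAP*

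**What the plan says.** **Missed appointments (protocol 5.5).** The site must telephone and "will try to make a new appointment within the established window period or an unscheduled appointment". If no appointment can be made, "the subject will be considered as loss of follow-up and will be asked about the presence of adverse events and the reason for leaving the" trial; this is the least that must be collected. The rule covers any appointment, so it includes Visit 1 (Day 7 ± 1).

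**Other early exits (5.5).** Follow-up after exit is explicitly required for one group only: "Subjects who are removed due to the presence of AEs will continue with the follow-up that is defined until the closure of their AE". A further sentence, on withdrawal of consent or major deviation, says that "the last visit, in which their withdrawal was determined, will be considered their final visit". Its opening condition is garbled, and it does not say whether anyone contacts the subject later.

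**Primary endpoints (Synopsis 1.1).** The first is "Incidence of unexpected PI-related AEs (Time of Assessment [TE]: days 7, 16 and 21"). The second is "Incidence of IP-related photophobia. (TE: 7th, 16th and 21st"). Section 7.4.5.4 has photophobia picked up by undirected AE questioning at Visit 1, the final visit and the safety call. The safety call (7.7.4) consists solely of "Evaluation of adverse events".

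**Analysis.** The primary population is "any subject who has received at least one dose of the investigational product (PRO-201) regardless of adherence to it or adherence to the protocol" (10.3.2.1). Section 10.4 provides no imputation. Section 5.2.2 lets the sponsor replace withdrawals and losses, without saying whether the replaced subject stays in the denominator.

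**The concern.** Loss to follow-up normally means that the subject cannot be reached. Here it is assigned to someone who can be asked about adverse events and about the reason for leaving. A missed clinic appointment does not prevent a telephone call five days after the final visit, and that call is already in the schedule.

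The rule can apply early. The Visit 1 window closes on Day 8. A subject dosing nightly from Day 1 then has about 14 − 8 = 6 doses left, and the Day-16 and Day-21 checks are still possible. Section 5.5 itself defines early discontinuation by a final evaluation that could not be completed, which is not yet true of this subject.

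The trial's conclusion rests on two proportions, judged against 10% and 15% in about 29 people. An unobserved period can hide an event but cannot create one. If such subjects remain in the denominator, any error favours the conclusions of safe and tolerable, and more so if people stop attending because of symptoms.

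**Working it through.** **Inputs**
- Base sample 24, raised by 20% for losses (10.1.2).
- Thresholds: 10% for unexpected related AEs and 15% for photophobia (3.2, 10.1.2).
- Dosing for 14 days (6.1.3); last AE check at Day 21 (1.3, 7.6.2).
- Assumed, not in the documents: the number lost, when they are lost, and the shape of the event risk over time.

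**The plan's own figure.** 24 × 1.2 = 28.8, rounded up to 29. This reproduces the stated 29. The implied loss allowance is 29 − 24 = 5 subjects.

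**Illustration 1: expected under-reading.** Suppose 5 of 29 have no contact after Day 7 and are kept in the denominator. With constant risk over T days and true cumulative incidence p:

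- risk seen by Day 7: r = 1 − (1 − p)^(7/T)
- expected observed incidence = (24p + 5r)/29

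| True p | T | r | Observed |
|---|---|---|---|
| 15% | 21 days | 1 − 0.85^(1/3) = 5.27% | (3.6 + 0.263)/29 = 13.3% |
| 15% | 14 days | 1 − 0.85^(1/2) = 7.80% | (3.6 + 0.390)/29 = 13.8% |
| 10% | 21 days | 1 − 0.90^(1/3) = 3.45% | (2.4 + 0.173)/29 = 8.9% |
| 10% | 14 days | 1 − 0.90^(1/2) = 5.13% | (2.4 + 0.257)/29 = 9.2% |

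Under the 21-day assumption, the true values that would just read as 15% and 10% are about 16.9% and 11.3%. The expected number of missed events is 5 × (0.15 − 0.0527) = 0.49 for photophobia and 5 × (0.10 − 0.0345) = 0.33 for unexpected related AEs. One subject is 1/29 = 3.4 percentage points.

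**Illustration 2: the counting convention.** Because the plan does not fix how incompletely followed subjects are counted, compare three conventions for the same observed data:

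| Observed events | Lost | Kept as no event | Excluded | Counted as events |
|---|---|---|---|---|
| 4 photophobia | 5 | 4/29 = 13.8% | 4/24 = 16.7% | 9/29 = 31.0% |
| 4 photophobia | 3 | 4/29 = 13.8% | 4/26 = 15.4% | 7/29 = 24.1% |
| 4 photophobia | 2 | 4/29 = 13.8% | 4/27 = 14.8% | 6/29 = 20.7% |
| 2 unexpected AEs | 5 | 2/29 = 6.9% | 2/24 = 8.3% | 7/29 = 24.1% |
| 2 unexpected AEs | 1 | 2/29 = 6.9% | 2/28 = 7.1% | 3/29 = 10.3% |

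With 4 photophobia events, keeping or excluding the lost subjects gives different answers against 15% once 3 are lost, but not with 1 or 2. Against 10%, these two conventions agree for 1 to 5 losses. Counting the lost as events can change the answer with a single loss.

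**The case against.** A reader might infer three stronger things, and the documents support none of them as written rules.

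- **That the remaining checks are cancelled.** No section cancels the Day-21 call, and 5.4 says that a safety call will be made. In the schedule the final visit comes before that call, so calling an early visit final does not by itself remove it. The AE questioning in 5.5 is described as minimum data, which does not rule out more contact.
- **That subjects who withdraw consent get no further contact.** The sentence is too unclear for that. It neither requires nor forbids contact.
- **That these subjects are scored as event-free.** Nothing says so. It is a likely result of a denominator of everyone dosed with no imputation, but the Synopsis plans 29 evaluable subjects and 5.2.2 allows replacement, so the denominator is open. Events reported earlier or on the missed-visit call would still count.

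It is also fair to say that early closure may be uncommon. An unscheduled appointment has no time limit, 7.7.5 allows unscheduled visits for AE reporting, and asking the reason for leaving suggests a subject who is departing. Illustration 1 puts the whole loss allowance at Day 7, and the expected loss is still under half an event.

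These points limit what can be claimed. They do not supply a requirement that is missing: 5.5 still assigns lost status to someone in contact, and nothing in it obliges the site to make the later checks for that person.

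**Conclusion.** The point holds as a weakness in the follow-up rule and a gap in the counting rule, not as a demonstrated bias. Section 5.5 gives lost status after one appointment that cannot be rebooked, despite contact, and mandates later follow-up only for AE removals. The analysis section does not say how dosed subjects with incomplete AE follow-up enter the two primary incidences.

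If they stay in the denominator, the direction is downward. Under the assumption of 5 losses at Day 7, the shift is about 1.2 to 1.7 percentage points at a true 15% and 0.8 to 1.1 at a true 10%. It would be smaller with fewer or later losses and larger if leaving is related to symptoms, which the documents do not allow one to quantify. The choice of convention can matter more than this average shift, because in a trial of 29 a few subjects can decide which side of 15% the result falls. The change is worth making because it is cheap and protects both primary endpoints.

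**What to change.** In 5.5:
- Treat a missed visit as a missed visit only.
- Attempt the Day-16 visit and the Day-21 safety call for every dosed subject who has not refused further contact.
- Reserve loss of follow-up for subjects who cannot be reached by the Day-21 call.
- Rewrite the sentence on consent withdrawal, and record at withdrawal whether telephone AE follow-up is still accepted.

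In 10.3.2.1 and 10.4:
- State how dosed subjects with incomplete AE follow-up are counted, and whether a replaced subject stays in the denominator.
- Beside each primary incidence, report the number of dosed subjects without Day-21 contact.
- Add a sensitivity analysis, for example with those subjects excluded and with them counted as events. The second is an upper bound, not an estimate.

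The cost is a wording change, a few calls of a type already scheduled, a slightly longer contact period for a few subjects, and possibly a slightly less favourable incidence.
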